8.6.5. Vital Signs

All vital signs will be summarized for the Safety Analysis Set for each cumulative dose group and for all groups combined. Descriptive summaries (mean, SD, median, minimum, and maximum) of actual values and changes from baseline values for systolic blood pressure (SBP), diastolic blood pressure (DBP), heart rate (HR), respiratory rate (RR), and oxygen saturation will be presented at each time point defined in Section 6.2.4.

Patients meeting the PCSA criterion value or change relative to baseline will be summarized for the Safety Analysis Set for each cumulative dose group and for all groups combined also.

In addition, a listing of each vital signs parameter will be presented for each patient.

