6.3.4 Vital Signs

Baseline values are defined as the last measurements taken before the first dose of oliceridine. Change from baseline will be defined as the post baseline value minus the baseline value. Vital signs will include blood pressure (BP), heart rate (HR), respiratory rate (RR), and temperature. Temperature will be measured at screening and baseline only.

Potentially clinically significant abnormal (PCSA) vital signs parameter criteria is defined below:

Parameter	Criterion value	Change relative to baseline
Systolic blood pressure (mmHg)	≥ 180 mmHg	25% increase
Systolic blood pressure (mmHg)	≤ 80 mmHg	25% decrease
Diastolic blood pressure (mmHg)	≥ 110 mmHg	25% increase
Diastolic blood pressure (mmHg)	≤ 40 mmHg	25% decrease
Pulse rate (bpm)	≥ 120 bpm	15 bpm increase
Pulse rate (bpm)	≤ 40 bpm	15 bpm decrease

Client: Trevena, Inc.
Version #: 1.0
Version Date: 20Dec2016

Protocol/CIP #: CP130-3003

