Windowed Time Point[a]	Change from Baseline	Baseline/ Observed/	Oliceridine <= 4 mg	Oliceridine >4 to 8 mg	Oliceridine >8 to 16 mg	Oliceridine >16 to 36 mg	Oliceridine >36 mg	All Treated Patients
			N=XXX	N=XXX	N=XXX	N=XXX	N=XXX	N=XXX
Baseline[b]								
n	Observed		xxx	xxx	xxx	xxx	xxx	xxx
Mean (SD)			xx.x (x.xx)	xx.x (x.xx)	xx.x (x.xx)	xx.x (x.xx)	xx.x (x.xx)	xx.x (x.xx)
Median			xx.x	xx.x	xx.x	xx.x	xx.x	xx.x
Min, Max			xx, xx	xx, xx	xx, xx	xx, xx	xx, xx	xx, xx
<T30 Minutes>								
n	Baseline[c]		xxx	xxx	xxx	xxx	xxx	xxx
Mean (SD)			xx.x (x.xx)	xx.x (x.xx)	xx.x (x.xx)	xx.x (x.xx)	xx.x (x.xx)	xx.x (x.xx)
Median			xx.x	xx.x	xx.x	xx.x	xx.x	xx.x
Min, Max			xx, xx	xx, xx	xx, xx	xx, xx	xx, xx	xx, xx
n	Observed		xxx	xxx	xxx	xxx	xxx	xxx
Mean (SD)			xx.x (x.xx)	xx.x (x.xx)	xx.x (x.xx)	xx.x (x.xx)	xx.x (x.xx)	xx.x (x.xx)
Median			xx.x	xx.x	xx.x	xx.x	xx.x	xx.x
Min, Max			xx, xx	xx, xx	xx, xx	xx, xx	xx, xx	xx, xx
n	Change		xxx	xxx	xxx	xxx	xxx	xxx
Mean (SD)			xx.x (x.xx)	xx.x (x.xx)	xx.x (x.xx)	xx.x (x.xx)	xx.x (x.xx)	xx.x (x.xx)
Median			xx.x	xx.x	xx.x	xx.x	xx.x	xx.x
Min, Max			xx, xx	xx, xx	xx, xx	xx, xx	xx, xx	xx, xx

[a] See section 6.2.3 of the SAP for windowed time point intervals.

[b] Baseline is the last non-missing value prior to the patient receiving the first dose of oliceridine.

[c] Only patients with both a baseline value and a windowed time point value are summarized at a given windowed time point.

Table 14.3.5.1.1
Potentially Clinically Significant Vital Signs
(Safety Analysis Set)

PCSA Criterion	Oliceridine <= 4 mg N=XXX	Oliceridine >4 to 8 mg N=XXX	Oliceridine >8 to 16 mg N=XXX	Oliceridine >16 to 36 mg N=XXX	Oliceridine >36 mg N=XXX	All Treated Patients N=XXX
Systolic Blood Pressure <= 80 mmHg	xxx (xxx.x%)	xxx (xxx.x%)	xxx (xxx.x%)	xxx (xxx.x%)	xxx (xxx.x%)	xxx (xxx.x%)
Systolic Blood Pressure >= 180 mmHg	xxx (xxx.x%)	xxx (xxx.x%)	xxx (xxx.x%)	xxx (xxx.x%)	xxx (xxx.x%)	xxx (xxx.x%)
Systolic Blood Pressure change from baseline > 25% increase	xxx (xxx.x%)	xxx (xxx.x%)	xxx (xxx.x%)	xxx (xxx.x%)	xxx (xxx.x%)	xxx (xxx.x%)
Systolic Blood Pressure change from baseline > 25% decrease	xxx (xxx.x%)	xxx (xxx.x%)	xxx (xxx.x%)	xxx (xxx.x%)	xxx (xxx.x%)	xxx (xxx.x%)
Diastolic Blood Pressure <= 40 mmHg	xxx (xxx.x%)	xxx (xxx.x%)	xxx (xxx.x%)	xxx (xxx.x%)	xxx (xxx.x%)	xxx (xxx.x%)
Diastolic Blood Pressure >= 110 mmHg	xxx (xxx.x%)	xxx (xxx.x%)	xxx (xxx.x%)	xxx (xxx.x%)	xxx (xxx.x%)	xxx (xxx.x%)

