Note: Percentages are based on the number of patients in each cumulative dose group.

Trevena, Inc.
Protocol CP130-3003CONFIDENTIAL
Page x of yTable 14.3.5.1.1 (continued)
Potentially Clinically Significant Vital Signs
(Safety Analysis Set)

PCSA Criterion	Oliceridine <= 4 mg N=XXX	Oliceridine >4 to 8 mg N=XXX	Oliceridine >8 to 16 mg N=XXX	Oliceridine >16 to 36 mg N=XXX	Oliceridine >36 mg N=XXX	All Treated Patients N=XXX
Diastolic Blood Pressure change from baseline > 25% increase	xxx (xxx.x%)	xxx (xxx.x%)	xxx (xxx.x%)	xxx (xxx.x%)	xxx (xxx.x%)	xxx (xxx.x%)
Diastolic Blood Pressure change from baseline > 25% decrease	xxx (xxx.x%)	xxx (xxx.x%)	xxx (xxx.x%)	xxx (xxx.x%)	xxx (xxx.x%)	xxx (xxx.x%)
Pulse Rate <= 40 bpm	xxx (xxx.x%)	xxx (xxx.x%)	xxx (xxx.x%)	xxx (xxx.x%)	xxx (xxx.x%)	xxx (xxx.x%)
Pulse Rate >= 120 bpm	xxx (xxx.x%)	xxx (xxx.x%)	xxx (xxx.x%)	xxx (xxx.x%)	xxx (xxx.x%)	xxx (xxx.x%)
Pulse Rate change from baseline > 15 bpm increase	xxx (xxx.x%)	xxx (xxx.x%)	xxx (xxx.x%)	xxx (xxx.x%)	xxx (xxx.x%)	xxx (xxx.x%)
Pulse Rate change from baseline > 15 bpm Decrease	xxx (xxx.x%)	xxx (xxx.x%)	xxx (xxx.x%)	xxx (xxx.x%)	xxx (xxx.x%)	xxx (xxx.x%)

Note: Percentages are based on the number of patients in each cumulative dose group.

Trevena, Inc.
Protocol CP130-3003

CONFIDENTIAL
Page x of y

Table 14.3.5.1.1 (continued)
Potentially Clinically Significant Vital Signs
(Safety Analysis Set)

PCSA Criterion	Oliceridine <= 4 mg N=XXX	Oliceridine >4 to 8 mg N=XXX	Oliceridine >8 to 16 mg N=XXX	Oliceridine >16 to 36 mg N=XXX	Oliceridine >36 mg N=XXX	All Treated Patients N=XXX
Oxygen Saturation < 90%	xxx (xxx.x%)	xxx (xxx.x%)	xxx (xxx.x%)	xxx (xxx.x%)	xxx (xxx.x%)	xxx (xxx.x%)

Note: Percentages are based on the number of patients in each cumulative dose group.

Table 14.3.6.1
Moline-Roberts Pharmacologic Sedation Scale (MRPSS) Total Score at Each Time Point
(Safety Analysis Set)

Windowed Time Point [a] Sedation	Oliceridine <= 4 mg N=XXX n (%)	Oliceridine >4 to 8 mg N=XXX n (%)	Oliceridine >8 to 16 mg N=XXX n (%)	Oliceridine >16 to 36 mg N=XXX n (%)	Oliceridine >36 mg N=XXX n (%)	All Treated Patients N=XXX n (%)
<Baseline [b]>						
1. None to Minimal	xxx (xxx.x)	xxx (xxx.x)	xxx (xxx.x)	xxx (xxx.x)	xxx (xxx.x)	xxx (xxx.x)
2. Anxiolysis	xxx (xxx.x)	xxx (xxx.x)	xxx (xxx.x)	xxx (xxx.x)	xxx (xxx.x)	xxx (xxx.x)
3. Moderate Sedation	xxx (xxx.x)	xxx (xxx.x)	xxx (xxx.x)	xxx (xxx.x)	xxx (xxx.x)	xxx (xxx.x)

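### The vital-sign PCSA table counts each limit and each change from baseline separately: no row requires both, and no row takes account of the baseline value

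*SAP*

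**What the plan says.** SAP 6.3.4 introduces its table with "Potentially clinically significant abnormal (PCSA) vital signs parameter criteria is defined below". Each line has a criterion value and, beside it, a change relative to baseline in the same direction. For example, pulse of 120 bpm or more sits beside "15 bpm increase", and systolic pressure of 80 mmHg or less beside a 25% decrease. No connective links the columns, and no condition is placed on the baseline value.

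SAP 8.6.5 supplies the connective: "Patients meeting the PCSA criterion value or change relative to baseline will be summarized".

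Mock Table 14.3.5.1.1 (Mock Data Displays) follows 8.6.5. The pulse limit "Pulse Rate >= 120 bpm" and the pulse change "Pulse Rate change from baseline > 15 bpm increase" are separate rows, as are "Systolic Blood Pressure >= 180 mmHg" and "Systolic Blood Pressure change from baseline > 25% increase". There is no row for limit plus change and no pooled row for any PCSA. The footnote sets the denominator: "Note: Percentages are based on the number of patients in each cumulative dose group".

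Neither section says whether PCSA uses every post-dose reading or only the one selected per analysis window under SAP 6.2.4. The change criteria in 6.3.4 carry no inequality sign, while the mock table uses strictly greater than.

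**The concern.** This is the only planned table that counts blood pressure and pulse against thresholds, and protocol 4.3.2 names symptomatic hypotension and tachycardia among the individual stopping criteria.

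A limit alone counts pre-existing states. A systolic pressure of 185 mmHg before and after dosing enters the high-pressure row with no change. Such patients can be enrolled: protocol 3.3.2 excludes surgical and medical patients only from ASA class IV upward, and the class III examples in protocol 9.3 include poorly controlled hypertension.

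A change alone counts ordinary variation. A pulse of 95 bpm at baseline and 78 later is a fall of 17 and enters the decrease row, although both values are well inside the limits.

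The patient who crosses a limit because of a material change, such as systolic pressure falling from 110 to 78 mmHg (32/110 = 29%), adds one to each of two rows. The two row totals do not give their overlap, so the table cannot say how many such patients there were.

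The columns are cumulative dose received. Protocol 3.1.4 leaves the number of readings to patient need and local practice. Patients treated longer may gather both more dose and more readings, so the change rows could rise across dose columns with no drug effect.

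**Working it through.** The plan states no expected PCSA rate, so there is no figure to reproduce. The wording check is set out above; what follows sizes the effect with no drug effect.

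**Assumptions, none from the documents.** Pulse readings are independent and normal, with mean 80 bpm and within-patient SD *w* of 6, 8 or 10 bpm. There is one baseline and *K* = 5, 10 or 20 post-dose readings. The between-patient SD is 0 or 12 bpm.

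**One reading.** P(change > +15) = 1 − Φ(15/(w√2)), which is 3.9%, 9.2% and 14.4% for *w* = 6, 8 and 10.

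**Any of K readings, one direction.** All changes share the same baseline, so P = ∫ φ(b)[1 − Φ(15/w + b)^K] db. The between-patient SD cancels. By symmetry the increase and decrease rows have the same rate.

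**Joint event.** Simulation of 300,000 patients per scenario, counting pulse ≥120 with a rise >15, or ≤40 with a fall >15, at the same reading.

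| w | K | Each pulse-change row | Joint, between-SD 0 | Joint, between-SD 12 |
|---|---|---|---|---|
| 6 | 5 | 13% | 0.00% | 0.3% |
| 6 | 10 | 20% | 0.00% | 0.5% |
| 6 | 20 | 29% | 0.00% | 0.9% |
| 8 | 5 | 27% | 0.00% | 1.1% |
| 8 | 10 | 38% | 0.00% | 1.9% |
| 8 | 20 | 49% | 0.00% | 3.3% |
| 10 | 5 | 39% | 0.03% | 2.8% |
| 10 | 10 | 51% | 0.06% | 4.8% |
| 10 | 20 | 63% | 0.13% | 8.2% |

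The joint columns cover both directions; each direction is about half.

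**Readings and dose group.** At *w* = 8, going from 5 to 20 readings raises each change row from 27% to 49% with no drug effect. The joint count (between-patient SD 12) also rises, from 1.1% to 3.3%, but from a much smaller base.

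**If only windowed values are used.** SAP 6.2.4 gives nine post-baseline windows for vital signs, plus an End-of-Treatment value, so *K* would be at most about 10 and the 20-reading rows would not apply.

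**Limit rows, systolic pressure.** With assumed mean/SD 130/18 or 140/20 mmHg, within-patient SD 8 or 12 and 2–8 readings, 16–48% of patients in the ≥180 row were already at or above 180 at baseline. The joint high-pressure event occurred in under 0.01% to 1.6%.

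**What the joint rule asks.** From a baseline of 180, a rise above 25% needs more than 180 × 1.25 = 225 mmHg. A fall from 100 to 78 is 22%, and a rise from 145 to 180 is 35/145 = 24%. Both cross a limit and neither meets the joint rule.

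**The case against.** The strongest reply is that the SAP made a documented choice. SAP 6.3.4 is silent, and 8.6.5 and the mock table agree on *or*, which suits a sensitive screen in a descriptive single-arm safety study. A reader might infer from the side-by-side layout that both conditions were meant and that the SAP contradicts itself. The text does not support that: the layout permits the reading but does not state it.

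A reader might also infer that a PCSA total is inflated, or that the fall from 110 to 78 is indistinguishable from a stable 185 or a pulse easing from 95 to 78. Neither holds. There is no pooled count, and these patients fall in different labelled rows. Pulse noise cannot enter the systolic ≤80 row. Because protocol 3.3.2 excludes haemodynamic instability, few treated patients should start at or below 80, so that row comes close to isolating the low-pressure event.

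Other outputs also cover the ground. Clinically significant abnormal vital signs that meet the definition are recorded as AEs (protocol 4.1.3) and tabulated under SAP 8.6.3. Values and changes are summarised by window, and Listing 16.2.6.1 shows the readings, so the joint event can be derived.

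All of this stands. It removes the case for calling the *or* rule an error or replacing it. It does not supply the missing joint count, which no planned table gives, or the missing baseline condition on the limit rows.

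**Conclusion.** The point holds as an inexpensive improvement to one safety table. Three facts come directly from the text: the combining rule is unstated in 6.3.4 and is *or* in 8.6.5; no row counts limit and change together; and no row separates patients already beyond a limit before dosing.

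The size rests on assumptions. Each pulse-change row would hold about 13–63% of patients with no drug effect. Pooling the two directions gives larger figures (73% rather than 38% at SD 8 with 10 readings), but the table does not pool them. Positive correlation between successive readings would lower the figures. A reader might infer that the joint pulse event is practically absent by chance. That follows only if every patient has the same mean pulse (0–0.13%); with a between-patient SD of 12 bpm it is about 0.3–8%. The joint row would be much cleaner than the change rows, but not free of noise.

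The link between reading count and dose column is possible, not shown by the documents.

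**What to change.** 1. Keep all existing single-criterion rows.
2. Add to SAP 8.6.5 and Table 14.3.5.1.1 one row per parameter and direction (systolic, diastolic, pulse; high and low: six rows) counting patients who meet the limit and the change at the same post-dose reading. State that all post-dose readings are used.
3. For each absolute-limit row, show separately the patients already beyond that limit at baseline.
4. State the combining rule, and the inequality for the change, identically in 6.3.4, 8.6.5 and the mock table.

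Do not make *and* the sole definition. It would drop cases such as systolic 100 to 78 or 145 to 180 mmHg, which cross a limit with a change just short of 25%.

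The cost is six more rows, the baseline split and a small amount of programming on data already collected. No planned output is lost.

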3.1.3 Predose period

Before dosing with oliceridine, vital signs (blood pressure, heart rate, respiratory rate), oxygen saturation, and somnolence/sedation will be measured. Somnolence/sedation will be measured using the MRPSS. During the predose period, an additional, post-surgical ECG will be performed only in surgical patients. Prior medications and AEs/SAEs will be recorded.

Pain intensity will be measured using a 0-10 point numeric pain rating scale (NPRS).

Predose period procedures will occur within 30 minutes before the first oliceridine dose. If the dosing period is delayed, predose period procedures (except the additional, post-surgical ECG performed only in surgical patients) will be repeated.

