3.5.5 Permitted and Prohibited Prior and Concomitant Medications

Prior medications are defined as those taken before the first dose of oliceridine. Concomitant medications are defined as those taken after the first dose of oliceridine.

Concomitant non-opioid analgesics are permitted. If a concomitant parenteral or oral opioid analgesic is used during the treatment phase, oliceridine treatment will cease, and the patient will be discontinued early and will undergo the end-of-treatment phase and follow-up phase procedures as scheduled.

Unless specifically prohibited, other medications are permitted, including common treatments of opioid-related adverse effects (eg, antiemetics, antacids, stool laxatives) and medications used to treat underlying medical conditions.

As with conventional opioids, prior and concomitant use of anxiolytics, sedative-hypnotics, or other potential CNS depressants requires elevated vigilance, consistent with the Joint Commission Sentinel Event Alert for the safe use of opioids in hospitals ([The Joint Commission, 2012](#)). Similarly, the perioperative use of epidural or intrathecal opioids prior to oliceridine requires cautious administration and increased monitoring, consistent with the American Society of Anesthesiologists Task Force on Neuraxial Opioids and the American Society of Regional Anesthesia and Pain Medicine Practice Guidelines for the Prevention, Detection, and Management of Respiratory Depression Associated with Neuraxial Opioid Administration ([American Society of Anesthesiologists 2016](#)).

Supplemental oxygen will be recorded as a prior and/or concomitant medication.

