6.3 Safety and Tolerability Analyses

The number and incidence of AEs/SAEs will be summarized overall and by severity and causality. MedDRA Version 19.0 will be used to classify all events with respect to system organ class and preferred term. WHODD (March 2016) will be used to categorize prior and concomitant medications. Summaries will include only treatment-emergent AEs (TEAEs) and will be summarized for the safety and tolerability analysis data set. Clinically significant changes in vital sign measurements, oxygen saturation measurements, somnolence/sedation scores, physical examination findings, and clinical laboratory assessments will be summarized via descriptive summary statistics.

Summary statistics for observed values and change from baseline values for vital sign measurements, oxygen saturation measurements, somnolence/sedation scores, physical examination findings, and clinical laboratory assessments will be summarized. Baseline values are defined as the last measurements taken before the first dose of oliceridine. SOWS total scores will be summarized.

Prior and concomitant medications will be summarized.

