6.3.8 Oxygen Saturation

Baseline values are defined as the last measurements taken before the first dose of oliceridine. Change from baseline will be defined as the post baseline value minus the baseline value.

Potentially clinically significant abnormal (PCSA) oxygen saturation criteria is defined below:

Client: Trevena, Inc.
 Version #: 1.0
 Version Date: 20Dec2016

Protocol/CIP #: CP130-3003

Parameter	Criterion value	Change relative to baseline
Oxygen Saturation	< 90 %	NA

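### The SpO2 tables ignore supplemental oxygen, so they can miss desaturation that oxygen averted and can show falls that come only from weaning

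*SAP*

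**What the plan says.** Protocol 6.3 asks for "Summary statistics for observed values and change from baseline values for vital sign measurements, oxygen saturation measurements", among other safety measures. SAP 8.6.5 carries this out by window: actual values and changes for the vital signs "and oxygen saturation will be presented at each time point defined in Section 6.2.4", by cumulative dose group and overall (mock Table 14.3.5.2). SAP 6.3.8 sets the baseline: "Baseline values are defined as the last measurements taken before the first dose of oliceridine". It attaches no condition on oxygen.

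SAP 8.6.5 adds a threshold display: "Patients meeting the PCSA criterion value or change relative to baseline will be summarized for the Safety Analysis Set". SAP 6.3.8 also introduces the threshold: "Potentially clinically significant abnormal (PCSA) oxygen saturation criteria is defined below". The criterion is below 90%, and the entry for change relative to baseline is NA. Mock Table 14.3.5.1.1 accordingly has a single row, "Oxygen Saturation < 90" per cent, with no time points and no oxygen split. The SAP 6.3.4 criteria cover blood pressure and pulse rate. Respiratory rate has none.

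Protocol 3.5.5 states: "Supplemental oxygen will be recorded as a prior and/or concomitant medication". Listing 16.2.2.2 shows medication start and stop date/time, dose, and whether the medication was given for an adverse event. Oxygen use is not among the subgroups in SAP 7.7, SAP 7.2 plans no covariates, and the vital signs listing (16.2.6.1) has no oxygen column.

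**The concern.** A saturation reading means one thing on room air and another on oxygen. Two distortions can follow from carrying out the plan as written.

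- **Masking.** Protocol 4.3.3.1 wants oxygen at hand during dosing. A patient whose saturation is drifting down may be given it before any value below 90% is recorded. That patient then counts as normal in the threshold row.
- **Weaning.** Protocol 3.1.3 says: "Predose period procedures will occur within 30 minutes before the first oliceridine dose". Protocol 3.5.2.2.1 names the post-anesthesia care unit as a dosing setting, so a surgical patient's baseline may be taken on oxygen. A later room-air reading then shows a fall that the drug did not cause. Some such patients may also enter the below-90% row.

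Safety is the primary objective, and Protocol 4.3.2 tells investigators to anticipate effects on respiration. Below 90% is the only respiratory threshold tabulated among the vital signs. If oxygen use differs between cumulative dose groups, the apparent dose pattern in these tables would be affected as well.

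**Working it through.** The plan has no figure to reproduce: it has no sample size calculation, no test and no error rate. The check is a reading of the text followed by two illustrations.

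**Reading**

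1. Oxygen enters as a medication record with times (Protocol 3.5.5; Listing 16.2.2.2).
2. SpO2 enters as a value with a collection time (Listing 16.2.6.1).
3. No section of the SAP and no mock table joins the two.
4. SAP 6.2.4 keeps one value per window, the one nearest the midpoint, for the summaries over time. A low reading away from the midpoint drops out of Table 14.3.5.2. The SAP does not say whether the threshold row uses all values or only the selected ones.

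**Illustration 1: masking**

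Inputs from the documents:
- N = 1000 treated (Protocol 6.1).
- h = 15% to 31%, the hypoventilation rates on the two oliceridine regimens of the phase 2 PCA study (Protocol 1.1). That study used other demand doses, and its definition included respiratory rate and effort.

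Assumed:
- d = 25% to 50%, the share of these who would fall below 90% without oxygen.
- s = 25% to 75%, the share of those given oxygen before such a value is recorded.

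Formula: missing from the row = N × h × d × s.

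- Low end: 1000 × 0.15 × 0.25 = 37.5 patients (3.75%) would fall below 90%. Of these, 37.5 × 0.25 = 9.4 are missing, leaving 28.1 tabulated (2.8%).
- High end: 1000 × 0.31 × 0.50 = 155 patients (15.5%). Of these, 155 × 0.75 = 116.25 are missing, leaving 38.75 tabulated (3.9%).

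Tabulated rates of 2.8% and 3.9% look alike, yet here they stand for 3.75% and 15.5%.

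**Illustration 2: weaning with no drug effect**

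Assumed: w = 20% to 80% of patients on oxygen at baseline and later weaned, and g = 1 to 3 points lost on weaning.

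Formula: mean change = -(w × g).

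- Low end: -(0.20 × 1) = -0.2 points.
- High end: -(0.80 × 3) = -2.4 points.

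Only N and h stand in the documents. The ranges show what is possible and are not estimates.

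**The case against.** The strongest reply is that respiratory safety does not rest on this one row. Protocol 1.3.1 defines safety as adverse event incidence, including events related to oxygen saturation. Protocol 4.1.3 has clinically significant abnormal assessments recorded as adverse events when they meet the definition, and SAP 8.6.3 summarises them by severity and relationship. The two deepest MRPSS levels, which describe possible or likely airway impairment, are tabulated by window. The study is single-arm and descriptive, so no test or decision rule hangs on these tables.

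Most of this stands, and it limits the point. It does not remove it. Under Protocol 4.1.1, signs anticipated for a surgical or medical patient are not recorded as adverse events unless worse than expected, and an intervention is not itself an adverse event. The SpO2 tables should be the objective check on that judgement.

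A reader might infer three stronger things that the documents do not support:

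- **That oxygen necessarily hides desaturation from the row.** A value below 90% recorded before oxygen starts may still count. Midpoint selection is stated for summaries over time, and Table 14.3.5.1.1 has no time points.
- **That the plan does nothing with oxygen beyond counting it in a medication table.** Listing 16.2.2.2 links a medication to an adverse event, and Listing 16.2.5.1 links back. Oxygen given for a recorded event can be traced for each patient.
- **That the comparison of surgical, medical and ED patients is distorted.** SAP 7.7 names initial setting as a safety subgroup, but the table list has no SpO2 table by setting.

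**Conclusion.** The point holds in a limited form, with moderate confidence. The plan records oxygen use with times and analyses SpO2 without it. The only respiratory threshold among the vital signs can therefore undercount desaturation pre-empted by oxygen, and the change table can show falls due to weaning. The information is unlinked in the analysis rather than lost.

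The change limb of the sentence in SAP 8.6.5 does not apply to SpO2. Weaning acts through Table 14.3.5.2 and, for some patients, through the below-90% row.

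It would be tempting to conclude that the below-90% rate is understated by a known amount. The documents do not allow that, because they give no rate of oxygen use. Masking lowers the row and weaning can raise it. Patients put on oxygen because they are desaturating may also have more low readings than the rest. The 9 to 116 patients and the -0.2 to -2.4 points rest on assumed fractions, and the net direction is unknown. This is a cheap improvement to the primary safety displays and does not invalidate them.

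**What to change.** In SAP 6.3.8 and 8.6.5 and Tables 14.3.5.2 and 14.3.5.1.1:

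1. Classify each SpO2 record as room air, on oxygen or unknown, from the recorded oxygen start and stop times only. SAP 7.3.2 sets a missing start time on the first-dose date to the time of first dose, which could make pre-dose oxygen look newly started. Assign unknown wherever that rule would impute the start time.
2. Show SpO2 below 90% by oxygen status at the reading. State that the row uses all recorded post-dose values, not only the midpoint-selected one.
3. Keep the planned change-from-baseline table for all patients and add a display by oxygen status at baseline. Do not restrict the table to readings whose oxygen status matches baseline. That would drop the on-oxygen readings of patients who came to need oxygen after dosing, which selects on a post-dose outcome.
4. Add a row for SpO2 below 90% or supplemental oxygen newly started after first dose, with a note that routine oxygen use also enters it.

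The cost is SAP and shell wording plus some programming, with no new data. The drawbacks are an unknown category, whose size depends on how completely oxygen times are recorded, and a composite row that is less specific than the threshold alone.
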